1 PROTOCOL SUMMARY

1.1 Synopsis

Protocol Title: A Phase 2 Study of Pembrolizumab (MK-3475) every 6 weeks (Q6W) in Participants with Relapsed or Refractory Classical Hodgkin's Lymphoma (rrcHL) or Relapsed or Refractory Primary Mediastinal Large B-cell Lymphoma (rrPMBCL)

Short Title: Phase 2 study of MK 3475 Q6W in rrcHL or rrPMBCL

Acronym: None

Hypotheses, Objectives, and Endpoints:

Hypotheses are aligned with objectives in the Objectives and Endpoints table.

In male and female, programmed cell death 1 protein (PD-1) naïve, participants ≥ 18 years of age with either

- rrcHL who have failed to respond or relapsed after ≥ 1 line of multiagent therapy (can include brentuximab vedotin), or who have failed to achieve a complete response (CR) or relapsed after auto-stem cell transplantation (SCT), or are ineligible for auto-SCT,

OR

- rrPMBCL who have failed to respond or relapsed after ≥ 2 lines of therapy (at least 1 of the prior lines of therapy must contain a rituximab-based regimen), or who have failed to achieve a CR or relapsed after auto-SCT, or are ineligible for auto-SCT:

Primary Objective	Primary Endpoint
To evaluate objective response rate (ORR), by cohort, rrcHL and rrPMBCL, as assessed by the investigator according to Lugano classification criteria [Cheson, B. D., et al 2014] in individuals treated with pembrolizumab Q6W.	Participants with complete response (CR) or partial response (PR).
Secondary Objectives	Secondary Endpoints
To evaluate objective response rate (ORR), by cohort, rrcHL and rrPMBCL, as assessed by blinded independent central review (BICR) according to Lugano classification criteria [Cheson, B. D., et al 2014] in individuals treated with pembrolizumab Q6W.	Participants with complete response CR or PR.

To evaluate duration of response (DOR), by cohort, rrcHL and rrPMBCL, as assessed by the investigator according to Lugano classification criteria [Cheson, B. D., et al 2014] in individuals treated with pembrolizumab Q6W.	The time from first documented evidence of CR or PR until disease progression or death due to any cause, whichever occurs first.
To evaluate duration of response (DOR), by cohort, rrcHL and rrPMBCL, as assessed by BICR according to Lugano classification criteria [Cheson, B. D., et al 2014] in individuals treated with pembrolizumab Q6W.	The time from first documented evidence of CR or PR until disease progression or death due to any cause, whichever occurs first.
To evaluate the pharmacokinetic (PK) profile, immunogenicity of pembrolizumab 400 mg Q6W.	-PK parameters of pembrolizumab including AUC, C _{max} and C _{min} . -Antidrug antibody levels.
To evaluate the safety and tolerability of pembrolizumab Q6W.	-Adverse Events (AEs). -Discontinuations due to AEs.

Overall Design:

Study Phase	Phase 2
Primary Purpose	Treatment
Indication	Relapsed and/or Refractory Primary mediastinal large B-cell lymphoma, Hodgkin's lymphoma
Population	PD-1 naïve adult participants with rrcHL, who have failed to respond or relapsed after ≥1 line of multiagent therapy (with or without brentuximab vedotin), or who have failed to achieve a CR or relapsed after auto-SCT, or are ineligible for auto-SCT OR PD-1 naïve adult participants with rrPMBCL who have failed to respond or relapsed after ≥2 lines of therapy, or failed to achieve a CR or relapsed after auto-SCT, or are ineligible for auto-SCT
Study Type	Interventional

Intervention Model	Single Group This is a single group, multi site study.
Type of Control	No Treatment Control
Study Blinding	Unblinded open-label
Blinding Roles	No blinding
Estimated Duration of Study	The Sponsor estimates that the study will require approximately 4 years from the time the first participant (or their legally acceptable representative) provides documented informed consent until the last participant's last study-related contact.

Number of Participants:

Approximately 60 participants will be allocated into 2 cohorts based on baseline disease as described in Section 6.3.1.

Intervention Groups and Duration:

Arm Name	Intervention Name	Unit Dose Strength(s)	Dosage Level(s)	Route of Administration	Regimen/ Treatment Period/ Vaccination Regimen	Use
Arm 1 Cohort 1 :rrcHL Cohort 2 rrPMBCL	Pembrolizumab (MK-3475)	25 mg/mL	400 mg	IV Infusion	Day 1, then Q6W up to 18 doses (approximately 2 years)	Test Product

Other current or former name(s) or alias(es) for study intervention(s) are as follows:
MK-3475.

Total Number of Intervention Groups/Arms	1 arm, 2 cohorts
Duration of Participation	
Each participant will participate in the study from the time that the participant provides documented informed consent through the final protocol-specified contact
 
After a screening phase of 28 days, each participant will be assigned to receive study intervention until one of the conditions for discontinuation of study intervention is met.
 
After the end of treatment, each participant will be followed for the occurrence of adverse events and spontaneously reported pregnancy.
 
Participants who discontinue for reasons other than radiographic disease progression will have posttreatment follow-up imaging for disease status until any of the conditions for discontinuation of imaging are met.
 
All participants will be followed for overall survival until death, withdrawal of consent, or the end of the study.

Study Governance Committees:

Executive Oversight Committee	No
Data Monitoring Committee	No
Clinical Adjudication Committee	No

There are no governance committees in this study. Regulatory, ethical, and study oversight considerations are outlined in Appendix 1.

[figure not shown]
Study Accepts Healthy Participants: No

A list of abbreviations is in Appendix 9.

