4 STUDY DESIGN

4.1 Overall Design

This is a Phase 2, nonrandomized, multisite, open-label study of the efficacy and safety of IV pembrolizumab 400 mg Q6W in adult participants with rrCHL or rrPMBCL. Participants should be PD-1 naïve.

Participants with rrCHL (Cohort 1) must have failed to respond or relapsed after at least 1 line of multiagent therapy (chemotherapy with or without brentuximab vedotin), or have failed to achieve CR or relapsed after an auto-SCT, or are ineligible for auto-SCT.

Participants with rrPMBCL (Cohort 2) must have failed to respond or relapsed after ≥ 2 lines of prior therapy, or failed to achieve a CR or relapsed after auto-SCT or are ineligible for auto-SCT. At least 1 of the prior lines of therapy must contain a rituximab-based regimen. Participants with rrPMBCL must not require urgent cytoreductive therapy.

The study design is summarized in [Figure 1](#). The planned objectives and endpoints are detailed in Section 3.

After Screening, approximately 60 participants will receive pembrolizumab 400 mg fixed dose administered Q6W for up to 18 cycles (approximately 2 years) until documented disease progression per investigator assessment according to Lugano classification or the participant meets 1 of the discontinuation criteria (Section 7.1).

Disease will be assessed every 12 weeks using the Lugano response criteria [Cheson, B. D., et al 2014] per investigator assessment.

Participants who discontinue treatment for reasons other than disease progression will have posttreatment follow-up for disease status until disease progression, initiating a non-study cancer treatment, withdrawing consent, death, or becoming lost to follow-up. All participants will be followed for OS until death, withdrawal of consent, the end of the study, or becoming lost to follow-up, whichever comes first.

AEs will be monitored throughout the study and graded in severity according to the guidelines outlined in the NCI CTCAE 5.0. After the end-of-treatment, each participant will be followed for AE monitoring (see Section 8.4). Participants who undergo allogeneic SCT within 2 years after their last dose of study treatment will be followed for ECIs for up to 18 months post-transplant. This additional follow-up for participants undergoing an allogeneic SCT within 2 years after their last treatment is necessary to provide data for a post-marketing requirement from the FDA.

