4.4 Beginning and End-of-Study Definition

The overall study begins when the first participant (or their legally acceptable representative) provides documented informed consent. The overall study ends when the last participant completes the last study-related contact, withdraws consent, or is lost to follow-up (Section 7.3). For purposes of analysis and reporting, the overall study ends when the Sponsor receives the last laboratory test result or at the time of final contact with the last participant, whichever comes last.

If the study includes countries in the European Economic Area (EEA), the local start of the study in the EEA is defined as First Site Ready (FSR) in any Member State.

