6.1 Study Intervention(s) Administered

The study intervention to be used in this study is outlined in [Table 3](#).

Country-specific requirements are noted in Appendix 7.

Table 3 Study Interventions

Arm Name	Arm Type	Intervention Name	Intervention Type	Dose Formulation	Unit Dose Strength(s)	Dosage Level(s)	Route of Administration	Regimen/ Treatment Period/ Vaccination Regimen	Use	IMP or NIMP/ AxMP	Sourcing
Arm 1 Cohort 1 :rrcHL Cohort 2 rrPMBCL	Experimental	Pembrolizumab (MK-3475)	Biological/Vaccine	Solution	25 mg/mL	400 mg	IV Infusion	Day 1, then Q6W up to 18 doses (approximately 2 years)	Test Product	IMP	Central by Sponsor

EEA=European Economic Area; IMP=investigational medicinal product; NIMP/AxMP=noninvestigational/auxiliary medicinal product.

The classification of IMP and NIMP/AxMP in this table is based on guidance issued by the European Commission and applies to countries in the EEA. Country differences with respect to the definition/classification of IMP and NIMP/AxMP may exist. In these circumstances, local legislation is followed.

All study interventions will be administered on an outpatient basis.

All products indicated in [Table 3](#) will be provided centrally by the Sponsor or locally by the study site, subsidiary, or designee, depending on local country operational or regulatory requirements.

For any commercially available product that is provided by the study site, subsidiary, or designee, every attempt will be made to source these supplies from a single lot/batch number. The study site is responsible for recording the lot number, manufacturer, and expiry date for any locally purchased product as per local guidelines unless otherwise instructed by the Sponsor.

Refer to Section 8.1.8 for details regarding administration of the study intervention.

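### Is an estimated study length of about 4 years too short for the follow-up after allogeneic transplant in Section 4.1?

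*Combined protocol and SAP*

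**What the plan says.** In Section 1.1 (Estimated Duration of Study), "The Sponsor estimates that the study will require approximately 4 years from the time the first participant" (or that person's representative) "provides documented informed consent until the last participant's last study-related contact". Both ends of the interval are therefore fixed, and the far end is a last contact, not a data cutoff.

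The pieces that fill this interval are:

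- Screening of 28 days (Section 1.1, Duration of Participation).
- Up to 18 doses at 6-week intervals, described as roughly two years (Section 6.1, Table 3).
- In Section 4.1, participants who "undergo allogeneic SCT within 2 years after their last dose of study treatment will be followed for ECIs for up to 18 months" after the transplant. The same section says this extra follow-up "is necessary to provide data for a post-marketing requirement from the FDA".
- Survival follow-up, for which Section 1.1 says: "All participants will be followed for overall survival until death, withdrawal of consent, or the end of the study".

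Section 4.4 defines the close: "The overall study ends when the last participant completes the last study-related contact", or withdraws consent or is lost to follow-up. It gives no calendar date.

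**The concern.** The transplant window and the follow-up after transplant together take 3.5 years, counted from the last dose. Set against a total of 4 years, that leaves half a year for all accrual, screening and treatment, although a full course of treatment alone takes about two years. The word approximately does not stretch over a gap of that size.

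The follow-up at stake is one the protocol itself ties to a regulatory requirement. If the sponsor closed the study near the 4-year mark, ECI follow-up would be cut short for some transplanted participants, mainly those enrolled late or treated longest. Four years is also the only overall length in the visible text, and survival follow-up runs to an end of study that has no other date. A reader could reasonably ask whether the timeline was set without the transplant follow-up in mind.

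**Working it through.** **Inputs.** Total 4 years and screening 28 days (Section 1.1); 18 doses every 42 days (Table 3); transplant window 2 years and follow-up 1.5 years (Section 4.1). A year is 365.25 days. The visible text gives no accrual period, so it is left at zero or varied as an assumption.

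**The plan's own figure.** Four years cannot be rebuilt without the accrual period. What can be shown is how much room it leaves. Screening to last dose for an 18-dose completer is 28 + 17 × 42 = 742 days = 2.03 years. Without a transplant, 4 − 2.03 = 1.97 years remain for accrual and follow-up.

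**The longest on-schedule path.**

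- Screening, 18 doses and the full transplant window: 2.03 + 2 = 4.03 years.
- Adding 18 months: 4.03 + 1.5 = 5.53 years for one participant with no accrual, or 1.53 years over the estimate.
- With an assumed accrual of 1 or 2 years: 6.53 or 7.53 years.

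**Who would lose follow-up if the study did stop at 4 years.**

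- A first-enrolled completer gets the full 18 months only if transplanted within 4 years − 1.5 years − 742 days = 171 days (0.47 year) of the last dose.
- A completer who consents more than 0.47 year after the first participant cannot get the full 18 months, even if transplanted on the day of the last dose.
- The whole 3.5-year span fits only if the last dose falls within 0.5 year (182.6 days) of first consent. For the first-enrolled participant, (182.6 − 28) / 42 = 3.68 intervals, so at most 4 doses. Five doses give 28 + 4 × 42 = 196 days = 0.54 year, and 0.54 + 3.5 = 4.04 years.

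**Paths that do fit.** Four doses followed by transplant 3 months after the last dose: 4 − 1.5 − 0.25 − (28 + 3 × 42)/365.25 = 1.83. The full 18 months is obtained by year 4 if consent comes no more than 1.83 years after the first participant. More generally, time from first dose to transplant must be at most 4 − accrual − 0.08 − 1.5. That is 2.42 years with no accrual, 1.42 years with 1 year of accrual and 0.42 year with 2 years (accrual assumed).

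**Does anything stop the study at 4 years?** Set side by side, the passages say no:

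| Place | What it fixes |
|---|---|
| Section 1.1 | An approximate forecast of total length |
| Section 4.1, survival follow-up | May stop at the end of the study |
| Section 4.1, ECI follow-up after transplant | Has its own length; no end-of-study stop is written |
| Section 4.4 | End of study is the last participant's last contact; no date |

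A participant still in ECI follow-up has contacts to come, so under Section 4.4 the study has not ended. The dependence runs from follow-up to study length, not the other way.

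**Does any analysis use the 4 years?** None in the visible part of Section 9. Response rate and duration of response are not tied to it, pharmacokinetic data are analysed once all participants complete Cycle 5 (Section 9.4.3), and no interim analysis is planned (Section 9.7).

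**The case for a change.** The strongest case for a change is that Section 1.1 does not describe its figure as an analysis date. It runs to the last study-related contact, and contacts after transplant are study contacts. On that reading the estimate should cover them, and it falls short by 1.53 years before accrual. The shortfall does not need the extreme path, because a completer who enrols half a year after the first participant is already outside. Dose interruptions, which the text after Table 5 allows, would only lengthen the path.

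The arithmetic stands, and so does the observation that 4 years does not contain the maximum follow-up. The step to a defect does not. The figure is a forecast, and a forecast need not equal the sum of every permitted maximum for a subgroup that may be small or empty; the documents give no transplant rate. The harm requires closure near 4 years, which no visible passage states and which Section 4.4 contradicts.

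The possible remedies add little. Restating the length as accrual plus about 5.5 years would replace an estimate with a worst case, and an incomplete one, since interruptions can extend it. Writing that the study stays open until the last ECI window closes would largely repeat Section 4.4.

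One practical question remains: how transplants up to 2 years after the last dose are found, and whether survival contact continues for everyone meanwhile. The places where that would be expected (the Schedule of Activities, Sections 8.4.1, 8.4.7, 8.11.4.3 and 8.11.5) are redacted, so their content cannot be counted as missing.

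**Conclusion.** No change follows. The estimate in Section 1.1 is about 1.5 years shorter than the longest on-schedule path for one participant, before accrual. It is an approximate forecast set against a conditional ceiling, and nothing has been miscalculated. Followed as written, Sections 4.1 and 4.4 keep the study open for the ECI follow-up, so the data for the regulatory requirement are not cut short. If transplants come late, the study will simply run longer than forecast.

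The effect on the response, duration-of-response, pharmacokinetic and safety analyses is nil. The conclusion rests on reading Section 4.4 as governing the end of the study, and on the redacted sections containing no calendar cutoff that overrides it. The number of participants on the long paths cannot be stated, because neither accrual nor the transplant rate is given.

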1.2 Schema

The study design is depicted in [Figure 1](#).

Figure 1 Study Diagram

[figure not shown]

BICR=Blinded Independent Central Review; Q6W=every 6 weeks; Q12W=every 12 weeks; rrcHL=relapsed and refractory classical Hodgkin's lymphoma; rrPMBCL=relapsed and refractory primary mediastinal B-cell lymphoma

[figure not shown]
a Imaging Q12W by investigator and BICR assessment according to Lugano classification.

1.3 Schedule of Activities

[figure not shown]
CCI

[figure not shown]
CCI

[figure not shown]
CCI

[figure not shown]
CCI

[figure not shown]
CCI

[figure not shown]
CCI

[figure not shown]
CCI

CCI

CCI

2 INTRODUCTION

2.1 Study Rationale

On 28-APR-2020, the FDA granted accelerated approval to the additional dosing regimen of 400 mg every Q6W for pembrolizumab across all currently approved adult indications, in addition to 200 mg Q3W dosing regimen. This study is being conducted upon the request of the FDA as a post-marketing requirement to provide additional data on the efficacy and safety of pembrolizumab 400 mg Q6W dosing regimen in participants with rrcHL and rrPMBCL. The results of this study will contribute to an understanding of the safety and efficacy of pembrolizumab administered IV, in a Q6W dosing regimen in the indications rrcHL and rrPMBCL.

2.2 Background

Pembrolizumab is a potent humanized IgG4 mAb with high specificity of binding to the PD-1 receptor, thus inhibiting its interaction with PD-L1 and PD-L2. Based on preclinical in vitro data, pembrolizumab has high affinity and potent receptor blocking activity for PD-1. Pembrolizumab has an acceptable preclinical safety profile and is in clinical development as an IV immunotherapy for advanced malignancies. Keytruda® (pembrolizumab) is indicated for the treatment of patients across several indications. For more details on specific indications refer to the IB.

2.2.1 Pharmaceutical and Therapeutic Background

The importance of intact immune surveillance function in controlling outgrowth of neoplastic transformations has been known for decades [Disis, M. L. 2010]. Accumulating evidence shows a correlation between tumor-infiltrating lymphocytes in cancer tissue and favorable prognosis in various malignancies. In particular, the presence of CD8+ T-cells and the ratio of CD8+ effector T-cells/FoxP3+ regulatory T-cells (T-reg) correlates with improved prognosis and long-term survival in solid malignancies, such as ovarian, colorectal, and pancreatic cancer, hepatocellular carcinoma, malignant melanoma, and renal cell carcinoma. Tumor-infiltrating lymphocytes can be expanded ex vivo and reinfused, inducing durable objective tumor responses in cancers such as melanoma [Dudley, M. E., et al 2005] [Hunder, N. N., et al 2008].

The PD-1 receptor-ligand interaction is a major pathway hijacked by tumors to suppress immune control. The normal function of PD-1, expressed on the cell surface of activated T-cells under healthy conditions, is to down-modulate unwanted or excessive immune responses, including autoimmune reactions. PD-1 (encoded by the gene Pdcd1) is an Ig superfamily member related to CD28 and CTLA-4 that has been shown to negatively regulate antigen receptor signaling on engagement of its ligands (PD-L1 and/or PD-L2) [Greenwald, R. J., et al 2005] [Okazaki, T., et al 2001].

The structure of murine PD-1 has been resolved [Zhang, X., et al 2004]. PD-1 and its family members are type I transmembrane glycoproteins containing an IgV-type domain responsible for ligand binding and a cytoplasmic tail responsible for the binding of signaling

molecules. The cytoplasmic tail of PD-1 contains 2 tyrosine-based signaling motifs, an immunoreceptor tyrosine-based inhibition motif, and an immunoreceptor tyrosine-based switch motif. After T-cell stimulation, PD-1 recruits the tyrosine phosphatases, SHP-1 and SHP-2, to the immunoreceptor tyrosine-based switch motif within its cytoplasmic tail, leading to the dephosphorylation of effector molecules such as CD3 ζ , PKC θ , and ZAP70, which are involved in the CD3 T-cell signaling cascade [Okazaki, T., et al 2001] [Chemnitz, J. M., et al 2004] [Sheppard, K-A, et al 2004] [Riley, J. L. 2009]. The mechanism by which PD-1 down-modulates T-cell responses is similar to, but distinct from, that of CTLA-4, because both molecules regulate an overlapping set of signaling proteins [Parry, R. V., et al 2005] [Francisco, L. M., et al 2010]. As a consequence, the PD-1/PD-L1 pathway is an attractive target for therapeutic intervention in rrcHL and rrPMBCL.

2.2.2 Preclinical and Clinical Studies

Please refer to the pembrolizumab IB for descriptions of the respective preclinical and clinical evaluations.

2.2.3 Ongoing Clinical Studies

Additionally, there is an expansive ongoing research program of clinical studies evaluating pembrolizumab in participants with a number of hematological and solid malignancies, including rrcHL and rrPMBCL. For further study details, please refer to the pembrolizumab IB.

2.2.4 Information on Other Study-related Therapy

Not applicable.

2.3 Benefit/Risk Assessment

It cannot be guaranteed that participants in clinical studies will directly benefit from treatment during participation, as clinical studies are designed to provide information about the safety and effectiveness of an investigational medicine.

However, reassurance of the benefit/risk profile for the proposed study is provided by the fact that pembrolizumab has marketing approval in the US and other countries for the following:

- Treatment of adult participants with rrcHL.
- Treatment of adult participants with refractory PMBCL, or who have relapsed after 2 or more prior lines of therapy.
- Note, KEYTRUDA® is not recommended for treatment of participants with PMBCL who require urgent cytoreductive therapy.
- Dosage of 400 mg Q6W across all adult indications.

In addition, interim results (based on data cutoff date 16-JAN-2020) from KEYNOTE-204, an ongoing, randomized, open-label, Phase 3 study of IV pembrolizumab 200 mg Q3W compared with IV brentuximab vedotin 1.8 mg/kg Q3W in participants with rrcHL who have failed to respond or relapsed on at least 1 prior multiagent chemotherapy regimen, demonstrate that pembrolizumab provides a clinically meaningful and statistically significant benefit in PFS compared with brentuximab vedotin (HR = 0.65 [95% CI: 0.48, 0.88], $p=0.00271$). ORR and DOR findings support the PFS results.

The efficacy of a pembrolizumab 400 mg Q6W dosing regimen is expected to be similar to the initially approved 200 mg Q3W regimen in the rrcHL and rrPMBCL indications (see Section 4.3).

Details regarding specific benefits and risks for participants participating in this clinical study may be found in the accompanying IB and informed consent documents.

